### 3.2 Exclusion Criteria

3.21 MGUS or smoldering myeloma.

3.22 Diagnosed or treated for another malignancy  $\leq$  2 years prior to registration or previously diagnosed with another malignancy and have any evidence of residual disease. **NOTE:** Patients with nonmelanoma skin cancer or carcinoma in situ of any type are not excluded if they have undergone complete resection.

3.23 Any of the following because this study involves an investigational agent whose genotoxic, mutagenic and teratogenic effects on the developing fetus and newborn are unknown:

- Pregnant women
- Nursing women
- Men or women of childbearing potential who are unwilling to employ adequate contraception

3.24 Other concurrent chemotherapy, or any ancillary therapy considered investigational. **NOTE:** Bisphosphonates are considered to be supportive care rather than therapy, and are thus allowed while on protocol treatment.

3.25 Peripheral neuropathy  $\geq$  Grade 2 on clinical examination or grade 1 with pain during the screening period.

3.26 Major surgery  $\leq$  14 days prior to registration.

3.27 Systemic treatment with strong CYP3A4 inducers (rifampin, rifapentine, rifabutin, carbamazepine, phenytoin, phenobarbital, St. John's wort)  $\leq$  14 days prior to registration.

3.28 Evidence of current uncontrolled cardiovascular conditions, including hypertension, cardiac arrhythmias, congestive heart failure, unstable angina, or myocardial infarction  $\leq$  6 months. Note: Prior to entry, any ECG abnormality at screening must be documented by the investigator as not medically relevant.

3.29a Radiotherapy  $\leq$  14 days prior to registration. **NOTE:** If the involved field is small, 7 days will be considered a sufficient interval between treatment and administration of the ixazomib

3.29b Known human immunodeficiency virus (HIV) positive.

- 3.29c Known hepatitis B surface antigen-positive status, or known or suspected active hepatitis C infection.
- 3.29d Any serious medical or psychiatric illness that could, in the investigator's opinion, potentially interfere with the completion of treatment according to this protocol.
- 3.29e Known allergies, hypersensitivity, or intolerance to corticosteroids, monoclonal antibodies or human proteins, or their excipients (refer to respective package inserts or Investigator's Brochure), or known sensitivity to mammalian-derived products.
- 3.29f Known GI disease or GI procedure that could interfere with the oral absorption or tolerance of ixazomib, lenalidomide or dexamethasone including difficulty swallowing.
- 3.29g Diarrhea > Grade 1, based on the NCI CTCAE grading, in the absence of antidiarrheals.

#### 4.0 Test Schedule

##### 4.1 Schedule of assessments

	Days Prior to Registration		Every 14 days (cycles 1 - 3) 	Every cycle, Induction 	Maintenance Phase: (every cycle) 
	≤30 days	≤14 days			
Complete medical history	X				
Adverse Event monitoring		X		X	X 
Physical exam, weight and vital signs		X		X	X 
Height		X			
Performance status (ECOG scale)		X		X	X 
CBC with diff.		X	X	X	X 
Prothrombin time (PT)	X				
Blood type and screen	X				
Chemistry group to include sodium, potassium, glucose, alkaline phosphatase; Total and Direct bilirubin; SGOT (AST);ALT serum creatinine, calcium		X	X	X	X 
sTSH, T3, T4	X				
LDH, Beta 2 -microglobulin, C-reactive protein	X				
Viral hepatitis panel including HBsAg, HB core antibody, and HB antibody	X 			X 	X 
Electrophoresis of serum and urine		X		X 	X 
Affected Immunoglobulin		X		X 	X 
Immunofixation serum and urine	X			X 	X 
Immunoglobulin free light chain		X		X 	X 
X-ray skeletal survey or WBLDCT	X			X 	X 
Bone marrow aspirate and biopsy	X			X 	X 
Research bone marrow and blood sample R,12	X			X 	X
Chest x-ray	X				

	Days Prior to Registration		Every 14 days (cycles 1 - 3) 	Every cycle, Induction 	Maintenance Phase:
	≤30 days	≤14 days			(every cycle) 
Serum pregnancy test		X 			
Patient Medication Diary (Appendix V) 				X	X
QOL questionnaire (Appendix VII)		X		X 	X 

- 1) All scheduled visits will have a window of  $\pm$  4 days unless otherwise stated
- 2) Immunofixation (IF) needed only in the absence of M-spike to document CR or sCR.
- 3) For women of childbearing potential only. Must be done  $\leq$  7 days prior to registration. Pregnancy tests for females of childbearing potential. A female of childbearing potential (FCBP) is a sexually mature female who: 1) has not undergone a hysterectomy or bilateral oophorectomy; or 2) has not been naturally postmenopausal for at least 24 consecutive months (i.e., has had menses at any time in the preceding 24 consecutive months). Pregnancy tests must occur within 10 – 14 days and again within 24 hours prior to prescribing lenalidomide for cycle 1. FCBP with regular or no menstruation must have a pregnancy test weekly for the first 4 weeks and then every 28 days while on therapy (including breaks in therapy); at discontinuation of lenalidomide and at Day 28 post the last dose of lenalidomide. Females with irregular menstruation must have a pregnancy test weekly for the first 4 weeks and then every 14 days while on therapy (including breaks in therapy), at discontinuation of lenalidomide and at Day 14 and Day 28 post the last dose of lenalidomide (see Appendix VI: Risks of Fetal Exposure, Pregnancy Testing Guidelines and Acceptable Birth Control Methods) potential only.
- 4) WBLDCT-whole body low dose CT, Every 12 cycles or if clinically indicated.
- 5) FLC is required only if used to assess disease response during active phase
- 6) At the end of 4 cycles, 12 cycles, after 12 and 24 cycles of maintenance (Cycles 24 and 36) and to document CR or disease progression.
- 7) The diary must begin the day the patient starts taking the medication and must be completed per protocol and returned to the treating institution.
- 8) Affected immunoglobulin refers to the baseline M-protein type, that is, IgG, IgA, IgD, or IgM. Not applicable if patient “non-secretory” or if patient has no heavy chain, i.e. light chain myeloma. Affected immunoglobulin is required after baseline only if it used for disease monitoring instead of SPEP (for e.g. IgA myeloma)
- 9) The QOL questionnaire will be filled out by the patient at baseline, every cycle for the first 4 cycles, and then every 3 cycles.
- 10) Urine Electrophoresis required only if used to assess disease response
- 11) Does not need to be repeated at Cycle 1 Day 1. Baseline values can be used for Cycle 1.
- 12) Not mandatory at baseline or disease progression
- 13) Patients enrolled prior to amendment 9 and within the past 6 months, will be need to tested as soon as feasible. Note: HBV-DNA testing required for patients with serologic evidence of prior HBV infection every 12 weeks during treatment, at EOT, and 12 weeks after last dose of study treatment.
- 14) **As of amendment 12** Required evaluations can be done through local facility, phone contact, or by local lab as applicable if patient is unable to return to Mayo facility and is approved by study chair.

R Research funded (see Section 19.0). Will be charged to study and not to patient's account.

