## 14.0 Biospecimens

### 14.1 Summary Table of Research Blood and Body Fluid Specimens to be collected for this Protocol

Table 14.1 Summary Table of Research Blood and Body Fluid Specimens to be collected for this Protocol										
Correlative Study	Mandatory or Optional	Blood or Body Fluid being Collected	Type of Collection Tube (color of tube top)	Volume to collect per tube (# of tubes to be collected)	Study Entry*	End of cycle 4, 12, 24, 36	At suspected CR	At PD*	Process at site? (Yes or No)	Temperature Conditions for Storage /Shipping
Flow cytometry for circulating plasma cells	Mandatory	Peripheral blood	ACD (yellow)	6 mL (3)	X	X	X	X	No	Cool Pak
Flow cytometry for MRD	Mandatory	Bone marrow aspirate	ACD (yellow)	6 ml (2)	X	X	X	X	No	Cool Pak

\* Samples at baseline and at time of disease progression are not mandatory

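### The Section 4.1 schedule marks the research marrow and blood sample for every maintenance cycle without a limiting note, while Table 14.1 schedules it only at Cycles 24 and 36; the two need reconciling.

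*Combined protocol and SAP*

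**What the plan says.** The Section 4.1 schedule has two adjacent marrow rows.

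- **Clinical row**, "Bone marrow aspirate and biopsy": the X carries note 6 in both the induction and the maintenance column.
- **Research row**, "Research bone marrow and blood sample": the X carries note 6 under induction but no note under maintenance. The maintenance column is headed "Maintenance Phase: (every cycle".

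Note 6 names the ends of Cycles 4 and 12, then the times "after 12 and 24 cycles of maintenance (Cycles 24 and 36) and to document CR or disease progression".

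The research row's label carries two notes of its own. Note 12 reads "Not mandatory at baseline or disease progression"; note R concerns funding.

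Table 14.1, the dedicated research-specimen table, labels both the blood and the marrow aspirate mandatory. It schedules them at study entry, at "End of cycle 4, 12, 24, 36", at suspected CR and at PD, with the footnote "Samples at baseline and at time of disease progression are not mandatory". Section 6.2 makes the correlative component mandatory, and inclusion criterion 3.19d requires willingness to give these samples.

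**The concern.** The schedule of assessments is the table from which sites order procedures. An unqualified X in an every-cycle column normally means that the procedure is due each cycle, and here the procedure is a mandatory marrow aspirate with a blood draw. A site working from Section 4.1 alone could take far more marrows than Table 14.1 asks for, and no use for the additional ones is stated. A site working from Table 14.1 would miss samples that Section 4.1 appears to require, so it is unclear what counts as a protocol deviation.

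**Working it through.** **Inputs**

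- Cycle length is 28 days, with induction in Cycles 1 to 12 and maintenance from Cycle 13 up to 36 months from registration (Section 7.1, both arms).
- Treatment starts 0 to 14 days after registration (Section 6.6).
- Scheduled sampling times are those in note 6 of Section 4.1 and in Table 14.1.

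**Step 1. The plan's own count.** Note 6 places maintenance marrows after 12 and 24 maintenance cycles. With 12 induction cycles, 12 + 12 = 24 and 12 + 24 = 36, so the note's Cycles 24 and 36 are right, and Table 14.1 gives the same two. That is 2 scheduled maintenance samples, plus one at suspected CR if it falls in maintenance and an optional one at PD.

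**Step 2. The literal count from Section 4.1.** One research marrow per maintenance cycle gives

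maintenance cycles = (days to month 36 − start lag) / 28 − 12, counting whole cycles.

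| 36 months taken as | Start lag | Cycles to month 36 | Complete maintenance cycles | Maintenance cycles begun |
|---|---|---|---|---|
| 36 × 365.25/12 = 1095.75 days | 0 days | 1095.75/28 = 39.13 | 39 − 12 = 27 | 28 |
| 1095.75 days | 14 days | 1081.75/28 = 38.63 | 38 − 12 = 26 | 27 |
| 36 × 30 = 1080 days | 0 days | 1080/28 = 38.57 | 26 | 27 |
| 1080 days | 14 days | 1066/28 = 38.07 | 26 | 27 |

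The literal count is therefore 26 to 27 complete cycles, or 28 at most if a cycle begun just before month 36 is counted. If 36 months were loosely read as 36 cycles, it would be 36 − 12 = 24. Every version is far above 2. At 27, the excess is 27 − 2 = 25.

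**Step 3. Does any other note limit the maintenance X?**

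- Note 1 (column heading) sets the visit window.
- Note 10 (column heading) concerns urine electrophoresis.
- Note 12 (row label) makes only the baseline and progression samples optional.
- Note R (row label) concerns who pays.

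None of them restricts the frequency. The limit appears only in note 6, which this cell lacks, and in Table 14.1.

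**Step 4. What the extra marrows could do to the analysis.** Section 2.31 asks for MRD negativity following induction. Section 16.331 assesses MRD in patients achieving CR, and Table 11.5 (notes a and k) has MRD testing start only at suspected CR, with CR required for an MRD-negative call. Section 16.33 labels the analysis exploratory. The primary endpoint is confirmed CR and does not use the research sample.

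**The case against.** The strongest reply is that the documents already answer the question. Note 6 sits on this same row, in the induction cell, and its text goes beyond induction to name the maintenance times. Table 14.1 repeats them, and the clinical marrow row carries note 6 in maintenance. Three places agree and one cell lacks a superscript, so most sites would probably infer the intent. That stands, and it lowers the likelihood of harm. It does not remove the conflict: an operative schedule for a mandatory invasive sample should not depend on inference from a neighbouring cell.

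The superscript might also have been lost when the PDF was read. This cannot be fully excluded, but the superscripts in the same row and in the row above survived.

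A reader might also infer that uneven sampling between sites would bias the MRD-negative rate, since a patient sampled more often has more chances to be counted as negative. The documents do not support that as a material effect. MRD assessment is confined to patients in CR, its objective is status after induction, the analysis is exploratory, and nothing shows that sites follow different tables.

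**Conclusion.** The inconsistency is real, and it is one of scheduling and protocol wording; it does not challenge a design decision. Section 4.1, read literally, calls for up to about 26 to 27 research marrows in maintenance, against 2 scheduled under Table 14.1.

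The upper figure is a ceiling. It assumes a patient who stays on treatment to month 36 and a site that applies the bare X in every cycle. Patients who leave for transplant (allowed any time after Cycle 4), lack of response, progression or toxicity would have fewer. The figure of 2 leaves out a suspected-CR sample and the optional PD sample. The same X covers the research blood, so the mismatch applies to that too, with less burden.

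What is at stake is patient burden and clarity about compliance. The primary endpoint, the decision rule, the sample size and the secondary endpoints are unaffected.

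**What to change.** Reconcile the research row of the Section 4.1 schedule with Table 14.1 so that both state one schedule for maintenance. The study team must confirm which is meant. If it is Table 14.1, as the matching note 6 indicates, adding the note 6 superscript to the maintenance X of that row is sufficient. If sampling every cycle were meant, Table 14.1 would need to say so and give its purpose.

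The superscript correction is a one-character edit that can go into the next amendment. It adds no procedures, and against a literal reading of Section 4.1 it removes many. It changes no analysis.

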## 4.2 Event Monitoring/Survival Follow-up

	Event Monitoring Phase 				
	q. 3 months until PD	At PD	After PD q. 6 months	Death	New Primary
Event Monitoring	X	X	X	X	At each occurrence

1. If a patient is still alive 3 years after registration, no further follow-up is required.

**5.0 Stratification Factors: None****6.0 Registration Procedures****6.1 Registration**

To register a patient, access the Mayo Clinic Cancer Center (MCCC) web page and enter the remote registration/ randomization application. The registration/randomization application is available 24 hours a day, 7 days a week. Back up and/or system support contact information is available on the Web site. If unable to access the Web site, call the MCCC Registration Office at [REDACTED] between the hours of 8 a.m. and 5:00 p.m. Central Time (Monday through Friday).

The instructions for the registration/randomization application are available on the MCCC web page [REDACTED] and detail the process for completing and confirming patient registration. Prior to initiation of protocol treatment, this process must be completed in its entirety and a MCCC subject ID number must be available as noted in the instructions. It is the responsibility of the individual and institution registering the patient to confirm the process has been successfully completed prior to release of the study agent. Patient registration via the registration/randomization application can be confirmed in any of the following ways:

- Contact the MCCC Registration Office [REDACTED] If the patient was fully registered, the MCCC Registration Office staff can access the information from the centralized database and confirm the registration.
- Refer to “Instructions for Remote Registration” in section “Finding/Displaying Information about A Registered Subject.”

**6.2 Correlative Research**

A mandatory correlative research component is part of this study, the patient will be automatically registered onto this component (see Sections 3.19c and 14.0).

**6.3 Verification**

Prior to accepting the registration, registration/randomization application will verify the following:

- IRB approval at the registering institution
- Patient eligibility
- Existence of a signed consent form
- Existence of a signed authorization for use and disclosure of protected health information

**6.4 IRB approval**

Documentation of IRB approval must be on file in the Registration Office before an investigator may register any patients. In addition to submitting initial IRB approval documents, ongoing IRB approval documentation must be on file (no less than annually) at the Registration Office [REDACTED] If the necessary documentation is not submitted in advance of attempting patient registration, the registration will not be accepted and the patient may not be enrolled in the protocol until the situation is resolved.

When the study has been permanently closed to patient enrollment, submission of annual IRB approvals to the Registration Office is no longer necessary.

6.5 Treatment requirements

**As of amendment 12:**

Treatment on this protocol must commence under the supervision of a hematologist from the enrolling institution.

6.6 Treatment start

Treatment cannot begin prior to registration and must begin ≤14 days after registration.

6.7 Pretreatment

Pretreatment tests/procedures (see Section 4.0) must be completed within the guidelines specified on the test schedule.

6.8 Baseline symptoms

All required baseline symptoms (see Section 10.5) must be documented and graded.

6.9a Study drug

Study drug is available on site.

6.9b Blood kits

Blood kit is available on site for this patient.

6.9c Patient questionnaire booklets

Patient questionnaire booklet is available on site; copies are not acceptable for this submission.

6.9d GCP

The clinical trial will be conducted in compliance with regulations (21 CFR 312, 50, and 56), guidelines for Good Clinical Practice (ICH Guidance E6), and in accordance with general ethical principles outlined in the Declaration of Helsinki; informed consent will be obtained from all participating patients; the protocol and any amendments will be subject to approval by the designated IRB prior to implementation, in accordance with 21 CFR 56.103(a); and subject records will be stored in a secure location and subject confidentiality will be maintained. The investigator will be thoroughly familiar with the appropriate use of the study drug as described in the protocol and Investigator's Brochure. Essential clinical documents will be maintained to demonstrate the validity of the study and the integrity of the data collected. Master files should be established at the beginning of the study, maintained for the duration of the study and retained according to the appropriate regulations.

## 7.0 Protocol Treatment

- Stem cell collection and transplant: Patients are allowed to collect stem cells at any time after completion of treatment on Cycle 4 if eligible for stem cell transplant. Details should be recorded on the Stem Cell Harvest form. If patient goes to transplant, they will go directly to event monitoring per Section 4.2 and the transplant should be reported on the event monitoring and Transplant and Engraftment forms. In the case that patients are unable to go to transplant due to other reasons, they can continue on study. In those cases, therapy may be interrupted for up to 4 weeks for the purpose of stem cell collection. Stem cells can be collected using standard institutional protocols. Any delay beyond 4 weeks should be discussed with the study PI prior to reinitiating protocol therapy.
- Lack of Response: Patients will go off treatment to event monitoring if an MR is not seen after 2 cycles and a PR is not seen after 4 cycles. Confirmation of MR or PR is not required.
- Dose modifications for toxicity are outlined in Section 8.
- An individual subject will be considered off-treatment following a 28-day safety follow-up period after the last cycle of treatment.

### 7.1 Treatment Schedule Arm A

Table 7.1			
Induction phase (Cycles 1-12)			
Drug	Route	Dose	Schedule Each cycle is 28 days
Ixazomib	Oral	4 mg	Days 1, 8 and 15
Lenalidomide	Oral	25 mg (if CrCl >60 ml/min)	Days 1-21
		10 mg (if CrCl 30-60 ml/min)	
Daratumumab	IV	16 mg/kg	Cycles 1 and 2: Days 1, 8, 15, 22
			Cycles 3, 4, 5, and 6: Days 1, 15
			Cycles 7 and beyond: Day 1
Dexamethasone	IV/ Oral*	40 mg	Days 1, 8, 15 and 22 Arm A: Cycles 1-12
* On days when daratumumab is given, dexamethasone is given IV over 15 minutes within 1 hour prior to daratumumab			
Maintenance Phase (Cycle 13 + up to 36 months from registration)			
Ixazomib	Oral	4 mg	Days 1, 8 and 15
Daratumumab	IV	16 mg/kg	Day 1
Cycle = 28 days			

NOTE: Once the creatinine clearance is >60 mL/min during the course of the treatment, lenalidomide can be increased to 25 mg.

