## 8.0 Dosage Modification Based on Adverse Events

Strictly follow the modifications in this table for the first **two** cycles, until individual treatment tolerance can be ascertained. Individual drugs can be dose reduced as per the table below depending on the adverse event attribution. If the toxicity is attributable to one drug, only that needs to be dose reduced. If overlapping toxicities are observed, the dose reductions can be alternated between the suspected drugs, starting with the drug most likely related to the adverse event. Thereafter, these modifications should be regarded as guidelines to limit to mild-to-moderate, but not debilitating, side effects. If multiple adverse events are seen, administer dose based on greatest reduction required for any single adverse event observed. Reductions apply to treatment given in the preceding cycle and are based on adverse events observed since the prior dose.

**NOTE: If ixazomib, lenalidomide or daratumumab is discontinued, the patient can continue on the other drugs, unless specified otherwise in the dose modification tables. If all three are discontinued, the patient will go to event monitoring (Section 4.2).**

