**ALERT: ADR reporting may be required for some adverse events (See Section 10)**

8.1 Dose Levels for each drug in the combination  
 (Based on Adverse Events in Tables 8.2-5)

**NOTE:** Toxicities attributable to dexamethasone should lead to dose reduction only for dexamethasone.

Table 8.1 Dose reduction steps				
Step	Ixazomib	Lenalidomide	Daratumumab	Dexamethasone
0	4 mg	25 mg	NA	40 mg
-1	3 mg	15 mg		24 mg
-2	2.3 mg	10 mg		12 mg
-3	Discontinue	5 mg		4 mg
-4	Discontinue	Discontinue		Discontinue

8.11 Instruction for initiation of a new cycle of therapy or restarting therapy after interruption during a cycle for toxicities

A new cycle of treatment may begin on the scheduled Day 1 of a new cycle if:

- The ANC is  $\geq 1000/\mu\text{L}$
- The platelet count is  $\geq 75,000/\mu\text{L}$
- Any other non-hematologic treatment -related adverse event that may have occurred has resolved to  $\leq$ Grade 1 or baseline severity.

If these conditions are not met on Day 1 of a new cycle, the subject will be evaluated weekly and a new cycle of therapy will be held until the toxicity has resolved as described above.

If any drug dosing was halted during the previous cycle and was restarted with a one-level dose reduction without requiring an interruption for the remainder of the cycle, then that reduced dose level will be initiated on Day 1 of the new cycle.

If any drug dosing was omitted for the remainder of the previous cycle or if the new cycle is held due to known hematologic toxicity newly encountered on the scheduled Day 1, then the new cycle will be started with a one-level dose reduction. If a new cycle of therapy cannot be restarted within 4 weeks of the scheduled Day 1 due to non-resolution of drug related toxicities, the patient will be removed from protocol therapy and will go to event monitoring.

→ → Use the NCI Common Terminology Criteria for Adverse Events (CTCAE) version 4.0\* unless otherwise specified ← ←

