### 8.3 Dose modifications for lenalidomide based on adverse events during a cycle

CTCAE System/Organ/Class (SOC)	ADVERSE EVENT	ACTION
Blood and lymphatic system disorders	febrile neutropenia associated with fever (temperature $\geq 38.5^{\circ}\text{C}$ )	
 
• Omit lenalidomide dose.
 
• Follow CBC weekly.
 
• If neutropenia has resolved to <math>\leq</math> grade 2 prior to Day 21 and fever has resolved, restart lenalidomide at next lower dose level and continue the cycle through Day 21. If febrile neutropenia is the only toxicity for which a dose reduction is required. G-CSF may be used and the lenalidomide dose maintained.
 

Investigations	If platelet count $<30 \times 10^9/\text{L}$ or ANC $<1.0 \times 10^9/\text{L}$ or ANC $>1.0 \times 10^9/\text{L}$ (up to LLN) with fever (temperature $>38.5^{\circ}\text{C}$ )	
 
• Omit lenalidomide dose.
 
• Follow CBC weekly.
 
• Hold anticoagulation until platelets <math>> 50,000</math>
 
• If platelet count resolves to <math>\leq</math> grade 2 prior to Day 21, restart lenalidomide at next lower dose level and continue the cycle through Day 21.
 
• If neutropenia has resolved to <math>\leq</math> grade 2 prior to Day 21, restart lenalidomide at next lower dose level and continue the cycle through Day 21. If neutropenia is the only toxicity for which a dose reduction is required. G-CSF may be used and the lenalidomide dose maintained.
 

Skin and subcutaneous tissue disorders	Rash maculo papular Grade 2 or 3.	
 
• Omit lenalidomide dose. Follow weekly.
 
• If the toxicity resolves to <math>\leq</math> grade 1 prior to Day 21, restart lenalidomide at next lower dose level and continue the cycle through Day 21.
 

	Any rash Grade 4	
 
• Discontinue lenalidomide. Remove patient from all study treatment.
 
• Go to event monitoring.
 

Nervous system disorders	Peripheral sensory Neuropathy Grade 3	
 
• Omit lenalidomide dose. Follow at least weekly.
 
• If the toxicity resolves to <math>\leq</math> grade 1 prior to Day 21, restart lenalidomide at next lower dose level and continue the cycle through Day 21.
 

CTCAE System/Organ/Class (SOC)	ADVERSE EVENT	ACTION

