	Grade 4	
 
Discontinue lenalidomide. Remove patient from all study treatment.
 
Go to event monitoring.
 

Immune system disorders	Allergic reaction Grade 2-3	
 
Omit dose. Follow at least weekly.
 
If the toxicity resolves to <math>\leq</math> grade 1 prior to Day 15 restart at next lower dose level and continue the cycle until Day 21.
 

	Grade 4	
 
Discontinue lenalidomide. Remove patient from all study treatment.
 
Go to event monitoring.
 

Vascular disorders	Thromboembolic event $\geq$ Grade 3	
 
Omit dose and start anticoagulation; restart at investigator's discretion (maintain dose level).
 

	Hyperthyroidism or Hypothyroidism $\geq$ grade 2	
 
Omit lenalidomide for remainder of cycle, evaluate etiology, and initiate appropriate therapy.
 
See Instructions for Initiation of a New Cycle and reduce the dose of lenalidomide by 1 dose level.
 

Other non-hematologic adverse event	Other non-hematologic toxicity $\geq$ Grade 3	
 
Omit lenalidomide dose. Follow at least weekly.
 
If the toxicity resolves to <math>\leq</math> grade 2 prior to Day 21, restart lenalidomide at next lower dose level and continue the cycle through Day 21.
 

Lenalidomide dose modifications for renal impairment developing during treatment, considered not related to lenalidomide

Renal Function	Dose
CrCl 30-60 ml/min	10 mg daily
CrCl $<$ 30 mL/min (not requiring dialysis)	15 mg every 48 hours
CrCl $<$ 30 mL/min (requiring dialysis)	5 mg once daily. On dialysis days, administer the dose after dialysis

\* Located at [REDACTED]

\*\* Use the following to describe actions in the Action column:

- Omit = The current dose(s) for the specified drug(s) during a cycle is skipped. The patient does not make up the omitted dose(s) at a later time
- Hold/Delay = The current dose(s) of all drugs during a cycle is delayed. The patient does make up the delayed dose(s) when the patient meets the protocol criteria to restart drugs.
- Discontinue = The specified drug(s) are totally stopped.

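### The lenalidomide renal-dose rules and the toxicity-reduction ladder are not reconciled, so a patient cut to 5 mg for toxicity can be assigned, or allowed, a higher dose when creatinine clearance changes

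*Combined protocol and SAP*

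**What the plan says.** Four parts of the protocol set the lenalidomide dose.

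- **Section 7.1, Table 7.1 (Arm A and Arm B).** The starting dose on Days 1-21 is 25 mg for CrCl above 60 mL/min and 10 mg for CrCl 30-60. The note under each arm's table reads: "Once the creatinine clearance is >60 mL/min during the course of the treatment, lenalidomide can be increased to 25 mg".
- **Section 8.1, "Table 8.1 Dose reduction steps".** There is one lenalidomide ladder for all patients: step 0 is 25 mg, -1 is 15 mg, -2 is 10 mg, -3 is 5 mg, and -4 is discontinuation. No starting step is labelled for a patient who begins on 10 mg.
- **Section 8.3, toxicity rows.** After most listed toxicities the instruction is to "restart lenalidomide at next lower dose level and continue the cycle through Day 21". Section 8.11 carries a reduced level forward into the next cycle. Section 8.0 gives the base for a cut: "Reductions apply to treatment given in the preceding cycle and are based on adverse events observed since the prior dose".
- **Section 8.3, renal table.** It is headed "Lenalidomide dose modifications for renal impairment developing during treatment, considered not related to lenalidomide". It lists 10 mg daily for CrCl 30-60, 15 mg every 48 hours for CrCl below 30 without dialysis, and 5 mg daily on dialysis. The doses are not labelled as maxima and do not refer to the patient's current step.

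Two further sentences in Section 8.0 bear on the point. When several adverse events occur together, the dose follows the largest cut that any one of them calls for. The Section 8 modifications are strict for the first two cycles and guidelines after that.

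**The concern.** The ladder sets the dose by tolerance; the note and the renal table set it by CrCl. A patient can come under both, and no sentence says which governs. For a patient already at the bottom of the ladder, the CrCl-based dose is the higher one.

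The situation is foreseeable. Section 3.12 admits patients down to CrCl 30 mL/min. Appendix I counts CrCl below 40 as a myeloma-defining event, and Section 15.27 lists renal failure among the very common lenalidomide toxicities. The note anticipates renal recovery and the renal table anticipates decline. Section 15.25 states that the drug is eliminated mainly by the kidney, so a dose that rises as clearance falls adds to exposure twice over. Two sites that each follow the text could also dose the same patient differently, which would blur the adverse-event and dose-delivery data within an arm.

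**Working it through.** The plan states no figure of its own on this point, so there is none to reproduce. The check crosses a toxicity-reduced dose with each CrCl rule.

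**Inputs.** Ladder doses 25, 15, 10 and 5 mg (Table 8.1); dosing on Days 1-21, which is 21 daily doses (Table 7.1); renal doses (Section 8.3 renal table); 25 mg on recovery (Table 7.1 note).

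**Formulas.** Daily dosing: cycle total = dose × 21. Every 48 hours: average per day = dose ÷ 2. As a cross-check, dosing on alternate days from Day 1 to Day 21 gives 11 doses. That count is an assumption, because the renal table does not restate the dosing days.

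**Cycle totals.** 25 × 21 = 525 mg; 15 × 21 = 315 mg; 10 × 21 = 210 mg; 5 × 21 = 105 mg; 15 mg every 48 hours = 15 × 11 = 165 mg.

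**Patient at 5 mg for toxicity, then CrCl changes:**

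| Change in CrCl | Rule | Dose given by the rule | Ratio to 5 mg daily |
|---|---|---|---|
| Falls to 30-60 | Renal table | 10 mg daily | 210/105 = 2.0 |
| Falls below 30, no dialysis | Renal table | 15 mg every 48 h, average 7.5 mg/day | 7.5/5 = 1.5 (165/105 = 1.57 by dose count) |
| Falls below 30, dialysis | Renal table | 5 mg daily | 105/105 = 1.0 |
| Rises above 60 | Table 7.1 note | 25 mg permitted | 525/105 = 5.0 |

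**How a patient reaches each row.**

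- Row 1: a 25 mg starter has had three reductions (25 to 15 to 10 to 5) before CrCl falls.
- Row 2: the same route applies. It also applies to a 10 mg renal starter after a single reduction, if a later fall from 30-60 to below 30 counts as impairment developing during treatment.
- Row 4: a 10 mg renal starter has had one reduction, to 5 mg, before CrCl recovers.

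**Is there a linking rule?** The largest-cut sentence in Section 8.0 is the nearest. It compares adverse events seen together. Renal recovery is not an adverse event, so the sentence does not reach row 4. For rows 1 and 2 the toxicity reduction is already in force when CrCl falls, and the renal table is confined to impairment judged unrelated to lenalidomide. Whether the sentence covers that sequence is unclear.

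**Where does a 10 mg starter enter the ladder?** Table 8.1 does not say. The Section 8.3 instruction is to go lower, and Section 8.0 takes the preceding cycle's treatment as the base. Together these point to the step below 10 mg. The gap is in labelling: the direction of the change is not in doubt.

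**The case against.** The strongest reply has four parts.

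- **The note is permissive.** It says the dose can be raised, and it sits under the table of starting doses, so its natural purpose is to lift the renal restriction on a 10 mg start. The carry-forward of a reduced level in Section 8.11 is worded as mandatory. This stands in part: the note does not direct 25 mg, and a careful investigator might not use it. But it makes no exception for a toxicity reduction, and the renal-decline rows do not depend on it.
- **The largest-cut sentence may already link the tables.** Creatinine increase is graded at every evaluation (Section 10.51), and the renal table lies inside Section 8, so falling CrCl could be read as one of several adverse events. That reading is reasonable for concurrent events. It does not clearly cover a reduction carried forward from earlier, and it says nothing about recovery.
- **Section 8 becomes guidance after two cycles.** Three reductions followed by new renal impairment would mostly occur in that later period, when physicians have discretion. This stands for the 25 mg starter. A renal starter needs only one reduction to reach 5 mg, which can happen in the strict period, and the note is in Section 7, outside the relaxation.
- **No frequency is given.** The share of patients with CrCl 30-60 is not stated, and each sequence needs a toxicity reduction and then a change in CrCl across a threshold. This stands and limits the severity.

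Two stronger readings are tempting. A reader might infer that a 10 mg starter reduced by one step lands on step -1, which is 15 mg. The text does not support this: "Reductions apply to treatment given in the preceding cycle and are based on adverse events observed since the prior dose", and a next lower level cannot be 15 mg for a patient taking 10 mg. A reader might also take 10 mg daily to 15 mg every 48 hours as an increase. Only the single administered dose rises; the average falls from 10 to 7.5 mg/day (165/210 = 0.79 per cycle).

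**Conclusion.** The concern holds as a failure to reconcile stated rules. For a patient at 5 mg for toxicity, the renal table read literally assigns 2 times that dose when CrCl falls to 30-60, and about 1.5 times when it falls below 30 without dialysis. For a renal starter at 5 mg, the note allows 5 times that dose on recovery.

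These sizes rest on reading the renal doses as assigned doses rather than ceilings, since the table does not call them ceilings. They also assume that the largest-cut sentence does not extend to a reduction already in force. The 1.57 figure further assumes 11 alternate-day doses.

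This is a should-fix point. A reader might infer that the protocol orders a 5-fold increase; it only permits one. Nor do the documents show any effect on the 36-patient decision rule in Section 16.21, or how many patients would be affected. A 10 mg starter has one reduction left where a 25 mg starter has three, but that follows from the starting doses and is not a contradiction.

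**What to change.** Reconcile the Table 7.1 note (both arms), Table 8.1 and the Section 8.3 renal table so that they state:

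1. which rule prevails when a renal adjustment and a prior toxicity reduction both apply, for both falling and recovering CrCl;
2. whether the Table 7.1 note applies to a patient who has had a toxicity reduction;
3. where a patient started on the renal dose enters the Table 8.1 ladder.

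The sponsor's clinical team decides the doses and the precedence; this review proposes neither. The cost is one text amendment to the two arms' notes and two tables. It needs no new assessments, because Section 4.1 already schedules serum creatinine every induction cycle and lenalidomide is given only in Cycles 1-12.
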